### **Brief Summary and Description**

The purpose of this study is to conduct a pilot study as part of a Career Development Award (K23) funded through NIH. We will recruit overweight or obese (OB) cigarette smokers ( $BMI \geq 25$ ) to participate in 8 weeks of either a self-regulation weight gain prevention intervention (SR; an intervention based on self-regulation approaches to produce and maintain weight loss shown to be effective for weight gain prevention) or lifestyle education (LE; attention-placebo control) followed by 8 weeks of smoking cessation treatment. We will conduct a small RCT with 60 OB smokers comparing SR to LE, with both conditions subsequently receiving smoking cessation counseling and combination nicotine replacement therapy to assess intervention feasibility and acceptability and obtain preliminary effect size data. Up to 60 OB smokers from the community will participate in 8 weeks of group weight gain prevention (self-regulation plus large changes in behavior) or lifestyle education (attention-placebo control) followed by 8 weeks of group smoking cessation treatment with nicotine replacement therapy as part of an RCT. Assessments will occur at baseline, week 9 (quit day), 1 month post-quit, 2 months post quit, and 3 months post-quit.

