### **Specific Aims**

We aim to conduct a small RCT with 60 OB smokers comparing SR to LE, with both conditions subsequently receiving smoking cessation counseling and combination nicotine replacement therapy to assess intervention feasibility and acceptability and obtain preliminary effect size data regarding the following hypotheses: Smokers in the SR vs. LE condition will have better biochemically verified point-prevalence abstinence from smoking at the end of smoking cessation treatment and at follow-ups, with a medium effect size. Smokers in the SR vs. LE condition will have less weight gain at the end of smoking cessation treatment and at follow-ups, with a medium effect size.

We will also examine potential mechanisms of action for efficacy of SR on improved smoking outcomes, expecting that: Smokers in the SR vs. LE condition will have greater increases in self-efficacy for managing weight and for quitting smoking and greater decreases in negative affect and delay discounting prior to quitting. Self-efficacy, negative affect, and delay discounting will be associated with abstinence at follow-ups.

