Counseling for smoking cessation. A combination of behavioral treatment and medication is recommended according to clinical practice guidelines. Treatment elements associated with greater odds of success such as support and problem-solving skills will be incorporated throughout the counseling. Participants will be introduced to smoking cessation counseling beginning at week 7. While weeks 7 & 8 remain predominantly focused on creating a weight loss buffer (SR) or learning healthy lifestyle information (LE), approximately 20 minutes of each of these sessions will be dedicated to preparing participants to quit smoking. This will include providing basic information about smoking and successful quitting (e.g., the addictive nature of smoking, the fact that smoking even a puff increases the likelihood of relapse, typical symptoms and duration of withdrawal, benefits of quitting, importance of removing cigarettes from the environment) and encouraging participants in their quit attempts. Participants will be asked to determine a plan for high-risk situations and will be taught behavioral self-management strategies (i.e., avoid, alter, alternative), and cognitive coping strategies such as using self-statements (e.g., benefits of quitting, statements of determination). Participants will be instructed to start using NRT lozenges beginning at week 6 (pre-quit). They will begin using combination NRT (patch + lozenge) on the morning of their Quit Day which coincides with their 9th treatment session (NRT procedures below). Post-quit sessions (weeks 9-16) will focus on reinforcing success, providing encouragement, coping with cravings, discussing reactions to quitting and to NRT, problem solving, dealing with slips, planning for high-risk situations, encouraging the use of social support, and noting benefits of quitting. A brief portion of each smoking cessation session will include continued discussion of self-regulatory weight gain prevention or healthy lifestyle education information. If conducted remotely, participants may be mailed a device to monitor their CO.

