Patient adherence. Physical activity will be assessed using the Paffenbarger Activity Questionnaire (PAQ). Diet will be assessed using a questionnaire assessing frequency of eating behaviors (consuming sugar sweetened beverages, eating fast food) with measurable changes following the use of self-regulation strategies associated with weight outcomes. NRT use. Utilization of NRT will be assessed post-quit through weekly self-report using calendars. Utilization of a fitness app (SR condition only) will be recorded (e.g., number of days for which any dietary tracking occurred) during the weight management portion of the intervention (weeks 1-8).

Intervention outcome effects. Weight: Participants will be weighed in street clothes, without shoes. Weight will be measured at baseline, Quit Day, and post-quit follow-up sessions via an electronic scale. Timeline Follow-Back (TLFB): During each post-quit assessment, participants will be asked to report on smoking since the last assessment. Seven-day point prevalence abstinence will be based on self-report (7 consecutive days of no smoking) and biochemical verification. Exhaled Carbon Monoxide (CO): Alveolar CO will be assessed via the iCOquit® Smokerlyzer® CO  $\leq$  6 ppm, to verify self-reported abstinence on Quit Day and at post-quit follow-up sessions.

Process measures. These measures of theoretical processes will be collected at baseline and week 9 to explore effects of treatment on putative mechanisms and subsequent outcome variables. Self-efficacy. Smoking Self-Efficacy Questionnaire (SEQ-12): has two six-item subscales that measure confidence in ability to refrain from smoking when facing internal stimuli (e.g., feeling depressed) and external stimuli (e.g., being with smokers). Weight-efficacy after quitting smoking (WEAQ): is a six-item scale that assesses confidence to prevent weight gain after quitting smoking. Mood. The Positive and Negative Affective Schedule (PANAS): is a 20-item mood inventory with two scales that assess positive and negative affective states. Delay Discounting. Monetary Choice Questionnaire (MCQ): is a 27-item questionnaire that assesses preferences for either a smaller, immediate reward or a larger, delayed reward in order to calculate how quickly a reward diminishes in value as a function of its delayed receipt.

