## **D. POSSIBLE RISKS TO PARTICIPANTS, PLAN TO MINIMIZE RISKS, ANTICIPATED BENEFITS OF PARTICIPATION**

### **Potential Risks**

Potential risks are minimal and include:

1. Nicotine withdrawal or discomfort following smoking cessation (likelihood high; seriousness low): Upon quitting smoking some individuals experience increases in cravings to smoke, irritability, anxiety, depression, or appetite, changes in sleep, difficulty concentrating, feelings of impatience or restlessness, coughing, dizziness, nausea, or sore throat.
2. Adverse side effects from NRT (likelihood low; seriousness variable): In some individuals, the use of nicotine patch is associated with local skin reactions, mild difficulty sleeping, mild anxiety, (rarely) vivid dreams or nightmares. Local skin reaction in up to 50% of patients, usually mild and self-limiting; rotating patch sites is recommended or discontinuing patch treatment (fewer than 5% of patients). Difficulty sleeping is mild; patients can remove the patch before bedtime and replace it in the morning. The same is true for vivid dreams. Mild anxiety similar to the effects of smoking a few cigarettes is sometimes reported; dosage can be lowered. Common side effects of nicotine lozenges include mouth or throat soreness, indigestion, heartburn, sour or upset stomach, or nausea. These are generally mild and transient. While NRT is intended for use in place of smoking as a smoking cessation aid, some participants may smoke in reduced amounts while using NRT. Research on the effects of using NRT concurrently with cigarette smoking have found no evidence of dangerous consequences of such a practice, including use of up to 42mg of NRT for 2 weeks prior to cessation while continuing to smoke ad libitum. If participants were to smoke while using NRT, they may experience nausea as a side effect.

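### The mechanism hypothesis concerns change before quitting, but the only post-baseline process measurement falls on Quit Day, and the supplied text does not ensure that it precedes the quit.

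*Combined protocol and SAP*

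**What the plan says.** All references are to the combined protocol and SAP.

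- **Hypothesis (Specific Aims).** SR is expected to produce larger gains in self-efficacy and "greater decreases in negative affect and delay discounting prior to quitting". The same variables are then expected to be associated with abstinence at follow-up.
- **Measurement times (Procedures, Process measures).** "These measures of theoretical processes will be collected at baseline and week 9 to explore effects of treatment on putative mechanisms". No other time point is given for SEQ-12, WEAQ, PANAS or MCQ.
- **What week 9 is (Brief Summary and Description).** "Assessments will occur at baseline, week 9 (quit day), 1 month post-quit", followed by months 2 and 3.
- **What happens that day (Procedures, Counseling for smoking cessation).** Patch plus lozenge starts "on the morning of their Quit Day which coincides with their 9th treatment session".
- **Smoking status that day (Procedures, Intervention outcome effects).** CO is used "to verify self-reported abstinence on Quit Day and at post-quit follow-up sessions". The Data Analysis Plan makes Quit Day the first time point for abstinence.
- **Analysis (Data Analysis Plan).** One set of regressions tests the effect of arm on the week 9 mechanism values, adjusted for baseline. A second tests the effect of the mechanisms on follow-up smoking. Neither mentions smoking status at the week 9 assessment.

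The supplied text gives no hour or completion window for the week 9 questionnaires relative to the last cigarette, the first patch or session 9. The assessment section points to a Table 1 schedule, which is not in the text available for review.

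**The concern.** The hypothesised quantity is the state reached at the end of the 8-week SR or LE programme, before the quit. The scheduled measurement is on the day of the quit. Someone who answers after stopping may already have some of the symptoms listed under Potential Risks, where "some individuals experience increases in cravings to smoke, irritability, anxiety, depression, or appetite" on quitting; several of these overlap with negative affect. Someone who meant to stop and did not may report lower confidence. The score would then combine the effect of the programme with the course of the first day.

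This matters in two places:

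1. **Arm to mechanism.** The week 9 contrast would include any difference between arms in first-day quitting, and so would not be purely the pre-quit change that was hypothesised.
2. **Mechanism to abstinence.** First-day success could raise the score and also make later abstinence more likely. An association could then appear even if the pre-quit value predicts nothing. That the week 9 score precedes the month 1 to 3 outcomes does not remove this common cause.

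The pilot is meant to supply effect sizes for a larger trial. A pre-quit value that was never collected cannot be recovered later.

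**Working it through.** The plan gives no figure on this point, so there is none to reproduce. The check has a timing part and an illustration.

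**Timing.** The hypothesis stops before quitting. The only post-baseline measurement is week 9, week 9 is Quit Day, and the patch starts that morning. A questionnaire finished before the last cigarette would match the hypothesis; one finished afterwards would not. The supplied text allows either.

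**Mechanism to abstinence.** All inputs are assumptions:
- 70% stop on Quit Day.
- Month 1 abstinence is 40% in those who stopped and 5% in those who did not.
- Those who did not stop score 0.5 SD lower that day.
- The pre-quit value has no true effect.

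Steps:
- P(abstinent) = 0.7 × 0.40 + 0.3 × 0.05 = 0.295.
- P(did not stop | abstinent) = 0.015 / 0.295 = 0.051.
- P(did not stop | not abstinent) = 0.285 / 0.705 = 0.404.
- Raw score difference = (0.404 − 0.051) × 0.5 = 0.177.
- Total SD = √(1 + 0.5² × 0.7 × 0.3) = 1.026, so the standardised difference is 0.177 / 1.026 = 0.172 SD.
- Implied correlation = 0.172 × √(0.295 × 0.705) = 0.08.

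Standardised difference with other stopping rates and shifts (40% and 5% kept):

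| Stop on Quit Day | Shift 0.3 SD | Shift 0.5 SD | Shift 1.0 SD |
|---|---|---|---|
| 60% | 0.13 | 0.21 | 0.39 |
| 70% | 0.11 | 0.17 | 0.32 |
| 80% | 0.08 | 0.12 | 0.24 |

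A second set of assumptions (50% or 70% stopping; later abstinence 40% versus 10%, or 30% versus 5%; shifts of 0.25 to 0.8 SD) gives correlations of about 0.03 to 0.13.

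**Arm to mechanism.** Induced arm difference = (arm difference in first-day abstinence) × (shift in SD). With assumed values of 0.2 and 0.5 this is 0.10 SD. Over 0 to 0.3 and 0.25 to 0.8 it runs from 0 to 0.24 SD.

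**Precision at n = 60**, ignoring clustering by treatment group and the baseline adjustment:
- Arms (30 versus 30): 1.96 × √(2/30) = 0.51 SD.
- Abstainers versus non-abstainers: 60 × 0.295 is about 18, leaving 42, so 1.96 × √(1/18 + 1/42) = 0.55 SD.

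The central artefact is therefore smaller than the 95% half-width in both analyses. It is a bias in the estimate, however, and a larger sample would not remove it.

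**The case against.** The strongest reply is that a reader might infer that the mechanisms are measured after the quit attempt has begun, and the documents do not say so. They do not give the order of questionnaires, patch and session within Quit Day, and Table 1 may settle it. Answers given early that day would sit close to the end of the 8-week programme. This stands, and the point is limited to the lack of any stated safeguard.

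Other replies:

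- **Verified abstinence on Quit Day does not show that people have already been abstinent for hours as part of the attempt.** Abstinence is defined over seven days, so the Quit Day value looks back over the pre-quit week. This stands.
- **Withdrawal may be slight by then.** Lozenges start at week 6 and the patch that morning. The documents give neither an onset time for symptoms nor the recall period of the affect scale. This stands, and the size of any shift is unknown.
- **The randomised contrast is sound.** A reader might infer that it is confounded. It is not, because both arms follow the same schedule. What may change is the quantity it estimates.
- **Slippage.** A reader might infer from the timeliness bonus, which covers only later visits, that the Quit Day questionnaires will drift. The payment is tied to the Quit Day assessment, and the lack of a bonus is not evidence of drift.
- **An earlier measurement is not clean either.** Lozenges, advice to cut down and quit preparation all precede Quit Day. This is true, but they are planned pre-quit steps in both arms, so a score from that period still fits the hypothesis.
- **The analysis is exploratory, and significance is disclaimed.** This limits the importance of the point. It does not answer it, because the aim is to obtain effect sizes.

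**Conclusion.** The mismatch is in the documents: a hypothesis about change before quitting, a single post-baseline measurement on Quit Day, and nothing in the supplied text that places the questionnaires ahead of the quit or adjusts for that day's smoking status. As written, the pre-quit hypothesis is not clearly tested.

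The consequence is modest. The regression of later smoking on the mechanisms is the more exposed analysis: about 0.17 SD in the central case and about 0.08 to 0.39 SD over the range tried. These figures rest wholly on assumed stopping rates, abstinence rates and score shifts, and on the assumption that scores are taken once first-day status is known. If every questionnaire is completed before quitting begins, the artefact is zero. This is a cheap improvement and not a flaw that threatens the trial.

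**What to change.** - In Procedures (Process measures) and the Data Analysis Plan, replace week 9 for SEQ-12, WEAQ, PANAS and MCQ with a window from session 8 to the day before Quit Day. The online survey platform already used for screening could deliver them.
- Keep weight, CO and smoking status on Quit Day.
- Do not set late questionnaires to missing; at n = 60 that discards data, and selectively. Flag any completed on or after Quit Day and record time since the last cigarette. Report a sensitivity analysis that excludes them or adjusts for smoking status at completion. Adjustment can also remove part of a true effect if the mechanism works through first-day success, so it should stay a sensitivity analysis.
- If Table 1 already requires completion before the quit, state that in the text and in the analysis plan.

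The cost is protocol wording and one extra short contact, with some risk of non-completion. The earlier score will still follow the pre-quit lozenges and quit preparation.

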#### Data Analysis Plan

Feasibility & Acceptability. Average monthly number of individuals screened and enrolled will show feasibility of screening and recruitment. The proportion of participants completing the final study assessment will show feasibility of retention. Response to SR & LE conditions. Attendance. The percentage of treatment sessions attended through week 10 (one week post-quit) will be calculated and compared between conditions; average attendance of  $\geq$  70% in both arms suggests good acceptability. Participant Feedback. Participant ratings of intervention satisfaction mean scores  $\geq$  3.5 (5-point scale) shows acceptability in each condition.

Intervention effects on treatment outcome variables: Based on ITT principles, all assigned participants will be used in analyses regardless of adherence and missing data. Participants with missing data will be assumed to have smoked and to have regained 0.3 kg/month (positive imputation) and analyses will be repeated using multiple imputation for sensitivity analyses. Generalized estimating equations (GEE) Group x Time analyses will be used for weight change and abstinence. Abstinence. The dependent variable of 7-day point-prevalence abstinence will be analyzed by time (Quit Day, 1, 2, 3-months post-quit) and conditions. Weight. The dependent variable of weight, will be analyzed by time (baseline, Quit Day, 1, 2, 3- months post-quit) and conditions. Secondary exploratory analyses will repeat the GEE analyses adding sex as a variable, and (separately) adding any/no weight loss at week 9 as a variable in predicting smoking abstinence.

Putative mechanisms will be examined using regression analyses to test the effects of treatment on proposed mechanistic variables at week 9, controlling for baseline values. Regression analyses will also test the effects of these proposed mechanisms on follow-up smoking outcomes. Notably, detection of statistically significant effects is not an objective in this limited-powered study.

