## **Procedures**

OB smokers (n=60) will be randomized to either a combined self-regulation plus large changes (SR) intervention in advance of smoking cessation treatment condition (n=30) or to a healthy lifestyle education (LE) in advance of smoking cessation treatment attention-placebo control condition (n=30) for 16 weeks. The study will include up to 18 groups each run in succession with approximately 4-6 participants recruited for each group in order to have 3-5 participants beginning each group. Groups will be randomly assigned to one of the two treatment conditions using a random number generator after participants have completed all pretreatment assessments. Participants will learn their condition assignment at the first treatment session. Feasibility and acceptability will be monitored. Assessment of smoking/abstinence and weight will be obtained at baseline, on Quit Day, and 1, 2, & 3-months post-quit.

Recruitment procedures- Participants will be recruited through print and electronic advertising (e.g., newspaper, magazine, listserv, websites, online ads), advertisements on buses or at bus stops, and via community outreach (e.g., providing study information and pamphlets to local physicians).

Initial screening: Interested individuals will be given several options for contacting the study and for completing initial eligibility screening depending on advertising modality (e.g., call the study telephone number, email the study email address, provide their contact information in an electronic interest form). Individuals will be given the option of either completing initial screening using an online screener or being contacted by study staff for telephone screening.

Phone screening: Individuals who are screened over the telephone will be contacted by study staff. They will be provided with a brief description of the study, and will be asked if they are interested in participating. Verbal consent will be obtained prior to the potential participant's completion of the phone screen using a bulleted consent form that includes key information. Individuals who indicate that they would like a copy of the consent document will be provided a copy via email.

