Interventions- The treatment will consist of 16 weekly, 60-minute, group sessions that will take place remotely using Zoom. The treatment will consist of 16, manualized, weekly sessions. The first 8 sessions will focus primarily on SR or LE (sessions 1-8) according to assigned condition with Quit Day preparations incorporated into weeks 7 & 8. The second 8 sessions (sessions 9-16) will focus primarily on smoking cessation and will also include brief discussions of weight and review of previously covered SR and LE topics according to assigned condition. Participants will be sent session handouts, a scale, and other intervention materials such as nicotine replacement therapy. In rare or extenuating circumstances, if a participant needs study materials in a time-sensitive way, they may be offered the opportunity to purchase these materials and be reimbursed via a ClinCard. The treatment groups will be led by study interventionists. All interventionists will be trained to provide treatment in both arms of the study. Study

interventionists will be postdoctoral fellows, clinical/counseling graduate students, or hired staff with backgrounds in clinical/counseling psychology, social work, nutrition, or another related field with intervention experience. Interventionists will be under the supervision of PI, a licensed clinical psychologist, with guidance from mentors as needed. Based on interventionist availability, if needed, the PI may also serve as an interventionist.

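### Does stopping the attendance benchmark at week 10 of a 16-week programme leave acceptability of the cessation phase unmeasured?

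*Combined protocol and SAP*

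**What the plan says.** The Data Analysis Plan, under Feasibility & Acceptability, introduces the attendance measure with the label "Response to SR & LE conditions" and continues: "The percentage of treatment sessions attended through week 10 (one week post-quit) will be calculated and compared between conditions". It then sets the benchmark, an average of at least "70% in both arms suggests good acceptability". A second acceptability criterion is a mean satisfaction rating of at least 3.5 on a 5-point scale in each condition.

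The Procedures section (Interventions) describes 16 weekly sessions. Sessions 1-8 deal mainly with SR or LE. For the rest, "The second 8 sessions (sessions 9-16) will focus primarily on smoking cessation", with brief review of SR or LE material. Combination NRT starts on the "Quit Day which coincides with their 9th treatment session".

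The Acceptability paragraph of Procedures says that attendance is recorded at every counseling session and that the percentage of participants completing each session is calculated, to give retention rates by treatment. Satisfaction is rated at week 9 and again at the end of treatment.

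**The concern.** The treatment lasts 16 weeks, but the only attendance threshold and the only stated between-arm attendance comparison stop one week after Quit Day. Six of the eight cessation sessions are left out. Acceptability is one of the pilot's aims (Specific Aims), and the pilot is meant to inform a larger trial (Project Purpose). A reader could take a pass on the 70% criterion as evidence that participants accept the whole programme, when it says almost nothing about whether they keep coming once they have tried to quit.

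The protocol also gives some support for treating SR and LE as 16-week conditions. Procedures describes assignment to an "attention-placebo control condition (n=30) for 16 weeks", and SR sessions in weeks 9-16 still include a weigh-in and a short discussion of weight.

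A second gap is the denominator for attendance. The rule that "all assigned participants will be used in analyses regardless of adherence and missing data" is written for the treatment outcome variables, and Procedures foresees that some recruits will not start: "approximately 4-6 participants recruited for each group in order to have 3-5 participants beginning each group".

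**Working it through.** **Inputs.** 16 sessions, split 8 and 8 (Interventions); Quit Day at session 9 (Counseling for smoking cessation); window through week 10 and 70% benchmark (Data Analysis Plan).

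**The plan's own figure.** Week 10 minus Quit Day week 9 is 1, so the description of week 10 as one week post-quit is correct.

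**Coverage of the window.**
- Sessions counted: 10/16 = 62.5%.
- Cessation sessions counted: sessions 9 and 10, so 2/8 = 25%.
- Sessions left out: 6/16 = 37.5%.

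**What a pass allows.** With window attendance w and attendance a at sessions 11-16, programme attendance is (10w + 6a)/16.
- w = 0.70, a = 0: 7/16 = 43.75%.
- w = 0.70, a = 1: 13/16 = 81.25%.
- Attending 7 of 8 pre-quit sessions and nothing after: 7/10 = 70% in the window, 7/16 = 43.75% overall.
- Attending all 8 pre-quit sessions and nothing after: 8/10 = 80% in the window, 8/16 = 50% overall.

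Late attendance needed for 70% of all 16 sessions (0.70 × 16 = 11.2 sessions) is (11.2 − 10w)/6:
- w = 0.8: 3.2/6 = 53.3%.
- w = 0.9: 2.2/6 = 36.7%.
- w = 1.0: 1.2/6 = 20%.

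These are bounds. The span from 43.75% to 81.25% only restates that late attendance may lie anywhere from 0 to 100%. It runs above 70% as well as below, so it shows no direction of error. As an arm average, the lower bound at 70% requires that nobody in the arm attends any session after week 10. The 7-of-8 pattern requires in addition that nobody attends on Quit Day or in the week after it.

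**Whether the missing summary is really missing.** Let N participants be in the denominator, n_s of them attending session s, and p_s = n_s/N. The average of p_1 to p_16 is (n_1 + … + n_16)/(16N), which is the 16-session attendance rate. The planned per-session percentages therefore contain it, and they also show where any fall begins, which the single average would hide.

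**What the window is meant to measure.** Three places describe SR and LE as chiefly an 8-week phase. The Brief Summary and Description has 8 weeks of SR or LE and then 8 weeks of cessation treatment. The Project Description does the same. The Patient adherence paragraph places the weight management portion in weeks 1-8. Cessation counseling and NRT are given to both arms. Ten weeks therefore cover all of the phase in which the arms mainly differ, plus Quit Day and the following week, which fits the label on the measure.

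**Denominator.** Groups are randomized after pretreatment assessments, and condition is disclosed at the first session. The protocol does not say whether the expected loss between recruitment and starting falls before or after assignment, so no shift in the 70% can be calculated from the documents.

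**The case for a change.** The strongest case for a change is that SR does not end at week 8. The colour-zone system is introduced only at the end of the first 8 weeks, is meant to help with most of the self-regulation steps, and then guides weight maintenance through the cessation phase. That maintenance work, aimed at post-cessation weight gain, falls mostly outside the window. The plan gives no reason for week 10. The per-session percentages carry no threshold and no stated comparison. End-of-treatment satisfaction comes only from those who respond, and completion of the final assessment is not session attendance. Adding 16-session attendance by arm would take a few sentences and no new data.

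The facts in this stand: the week-10 choice is unexplained, some SR content lies beyond it, and no attendance benchmark applies there. The case for revising the plan does not. The added figure would be an average of percentages already planned. Holding it to 70% would create a criterion the plan never set, on a measure that partly reflects drop-out after a failed quit attempt and so describes response to SR and LE less well than the week-10 figure. Allowing statements about the whole programme only on that figure would also set aside the satisfaction criterion that the plan does specify at the end of treatment.

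**Conclusion.** The counts are right: the benchmark covers 10 of 16 sessions and 2 of 8 cessation sessions. No change is needed. The window is a reasonable choice for a measure labelled as response to SR and LE. Later attendance is recorded and summarised session by session, and end-of-treatment satisfaction has its own criterion. The effect is confined to how one descriptive statement reads. The plan says only that 70% suggests good acceptability, attaches no progression rule to it, and states that detecting significant effects is not an objective. No estimate of abstinence or weight depends on it.

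Two details remain open, the reason for week 10 and the attendance denominator. An analyst would ordinarily fill the second by counting everyone assigned and saying so. This conclusion assumes that the per-session percentages are reported for all 16 sessions and shown by arm, which is the natural reading of retention rates specific to treatment. It also assumes that the week-10 figure is not presented as acceptability of the full programme.
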